**Table HMGW.6.14 Definition of Subgroup Variables**

Subgroup Variable	Categories
1. Gender	1. Female or Male
2. Race Origin	2. White American Indian or Alaska Native Asian Black or African American Native Hawaiian or Other Pacific Islander Multiple
3. Baseline Pain Severity	3. ≤6 vs. >6 on BPI average pain severity at baseline
4. Family history of Fibromyalgia	4. Yes/No
5. Onset age of Fibromyalgia (years)	5. ≤12 vs. >12
6. Comorbid MDD	6. Yes/No
7. Comorbid GAD	7. Yes/No
8. Country	8. Country name
9. NSAID use (ongoing, concurrent regimen)	9. Yes/No

Abbreviations: BPI = Brief Pain Inventory; MDD = major depressive disorder; GAD = generalized anxiety disorder; vs. = versus, NSAID = non-steroidal anti-inflammatory drugs.

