## **5.2. Determination of Sample Size**

Approximately 184 patients will be randomized in a 1:1 ratio to the duloxetine and placebo treatment groups. This study is to assess the difference of the mean change in BPI average pain severity from baseline to the last time point (Visit 8, Week 13) in Study Period II between treatment groups. Assuming that there will be some missing post-baseline data, and about 81% completion rate at acute phase by Visit 8 or Week 13, this sample size will provide at least 80% power to detect the treatment difference of 1.0 point with  $\alpha=.05$ . All the parameters used in the sample size calculations were based on the MMRM analysis of data from 3-month, placebo-controlled, acute treatment period in 2 adult FM studies: Study F1J-MC-HMCA and Study F1J-MC-HMCJ.

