#### 6.1.2. General Considerations

Efficacy and safety analyses will be done on an intent-to-treat (ITT) basis unless otherwise specified. An intent-to-treat analysis is an analysis of data by the groups to which patients are assigned by random allocation, even if the patient does not take the assigned treatment, does not receive the correct treatment, or otherwise does not follow the protocol.

All efficacy and safety analyses of continuous measures will include randomized patients with both a baseline and at least one post-baseline value for the variable being analyzed. For efficacy and continuous safety variables, baseline is defined as the last measurement taken at, or prior to the visit where the study period begins; endpoint is defined as the last non-missing measurement for the study period of interest. Table HMGW 6.1 provides baseline and post-baseline definitions for all variables.

Statistical analyses will be carried out for Study Period II, III, and IV (SP II-IV). All tests of hypotheses will be evaluated based on a two-sided significance level of 0.05 unless otherwise specified. No adjustments for multiple comparisons will be made.

For SP II, a patient's treatment group will be determined by the treatment to which the patient is randomized: either duloxetine (DLX) or placebo (PLA).

For SP III, the following treatment groups will be determined by the randomized treatment at SP II and extension phase treatment at SP III:

PLA/DLX: patients who are randomized to placebo at SP II and who enter SP III and take duloxetine.

DLX/DLX: patients who are randomized to duloxetine at SP II and who enter SP III and take duloxetine.

No statistical comparisons will be conducted to compare the two treatment groups PLA/DLX and DLX/DLX during SP III unless otherwise noted. For continuous measures, when appropriate, within treatment testing of change from baseline for selected safety and efficacy measures will be conducted for SP III.

For SP II/III, one treatment group will be determined by the randomized treatment at SP II:

DLX: patients who are randomized to duloxetine at SPII, including patients who may have discontinued early at SPII or who enter SPIII.

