### 6.1.15. Subgroup Analyses

Some of the baseline severity of illness will be summarized and analyzed by comorbid diagnosis subgroup, which includes: CDI by MDD and non-MDD, CGI-Severity: Mental Illness by MDD/GAD and non-MDD/GAD, and MASC by GAD and non-GAD.

Suicide-related ideation and behavior, treatment-emergent suicidal ideation and behavior will also be analyzed by the following subgroups: patients with or without comorbid MDD;  $\geq$  or  $<$  the baseline median CDI score for the study. The Fisher's exact test will be used to overall compare the proportion of suicide-related events between the treatment groups. A logistic

regression model with factors of treatment, subgroup and treatment-by-subgroup will be performed to compare the proportion accounting for the subgroup effect.

For the BPI average pain severity, a subgroup analysis will be conducted for Study Period II. Table HMGW.6.14 lists the subgroup analysis variables by which the analyses performed.

To analyze a specific subgroup's impact, change from baseline to endpoint (LOCF and BOCF) in BPI average pain will be analyzed using an ANCOVA model with all the terms described generally in Section 6.1.2 and 6.1.3 with additional terms of the subgroup and the subgroup-by-treatment interaction. The primary statistical test will be for the treatment-by-subgroup interaction, which will be tested at the significance level of 0.05.

Furthermore, treatment group differences will be evaluated within each category of a subgroup regardless of the significance level of the treatment-by-subgroup interaction. For the subgroup of Race Origin, all the categories that have <10% of the patients in the study will be combined in the analysis. For the subgroup of NSAIDs use, the NSAIDs use is based on concomitant medication took during study and medical review.

Subgroup analysis for other efficacy and safety variables will be conducted as deemed appropriate and necessary.

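### Effect modification by baseline pain, onset age and CDI is tested only after each numeric measure is cut in two, which costs the interaction test information

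*SAP*

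**What the plan says.** Section 6.1.15 analyses change in BPI average pain (LOCF and BOCF) by ANCOVA, adding a subgroup term and its interaction with treatment to the general model. For these analyses, "The primary statistical test will be for the treatment-by-subgroup interaction, which will be tested at the significance level of 0.05". Table HMGW.6.14 defines baseline pain as "≤6 vs. >6 on BPI average pain severity at baseline" and onset age of fibromyalgia as two groups divided at 12 years. Neither has a numeric version in the subgroup plan.

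CDI is not in that table. Earlier in 6.1.15, suicide-related outcomes are compared between patients at or above and patients below "the baseline median CDI score for the study", using Fisher's exact test and a logistic model with treatment, subgroup and their interaction.

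All three measures are available as numbers. Baseline BPI average pain must be at least 4 (Table HMGW.6.2), onset is recorded as an age (6.1.8), and the CDI total is a sum of 27 items (Table HMGW.6.3). The ANCOVA in 6.1.2 and 6.1.3 already carries the baseline value as a covariate, but only as a main effect.

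**The concern.** In the BPI subgroup model, baseline pain enters as a number for its main effect and as two categories for its interaction with treatment, which is the term being tested. The categories treat scores of 4 and 6 as alike and scores of 6 and 7 as different. Section 6.1.15 gives no reason for cutting at 6, at 12 or at the median.

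Interaction tests are weak in a trial sized for an average effect. Cutting the modifier weakens them further, so the plan is more likely to report no effect modification when the effect does change with severity or onset age. For CDI, the cut point also depends on the sample that happens to be enrolled.

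**Working it through.** **1. Inputs from the SAP.** Section 5.2: "Approximately 184 patients will be randomized in a 1:1 ratio to the duloxetine and placebo treatment groups"; "this sample size will provide at least 80% power to detect the treatment difference of 1.0 point with" alpha 0.05; and "about 81% completion rate at acute phase by Visit 8 or Week 13". Section 6.1.2 sets tests at a "two-sided significance level of 0.05 unless otherwise specified". The SAP does not state the SD, the distributions of the three modifiers, any interaction size or any rate of suicide-related events.

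**2. The plan's own figure.** Section 5.2 takes its parameters from earlier adult studies without printing the SD, so 184 cannot be reproduced independently. The implied SD follows from SD = 1.0 × √(n/2) / (1.960 + 0.842), with n per arm:
- Completers only, n = 92 × 0.81 = 74.5: √37.26 / 2.802 = 2.18.
- All randomized, n = 92: √46 / 2.802 = 2.42.

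I use 2.18–2.42 as the assumed SD of change.

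**3. Information kept by a cut.** If the effect changes linearly with modifier X, the cut version keeps the fraction r², the squared correlation between X and its indicator:

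r² = p(1 − p)(m₁ − m₀)² / Var(X),

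where p is the share above the cut and m₁, m₀ are the means above and below it.

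Example for baseline pain, assuming integer scores 4–10 with mean 6.57 and SD 1.41: p = 0.51, m₁ = 7.72, m₀ = 5.38, so r² = 0.51 × 0.49 × 2.34² / 1.41² = 0.69, a loss of 31%.

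Over the assumed distributions:
- Baseline pain, mean about 6–7: loss 30–36%. When few patients exceed 6 (12–19%): 40–52%.
- Onset age, mean 10.5–13.5 and SD 1.5–3: loss 32–66%, about 34% if the cut falls at the median.
- CDI median split: loss 1 − 2/π = 36% if normal, 40–45% if right-skewed.

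**4. Power for baseline pain.** Let b be the change in treatment effect per SD of baseline pain. Then z = b√N / (2 × SD), and the cut version has z√r². Power is Φ(z − 1.96), the other tail being negligible except for the smallest b, where it is included.

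Example: b = 0.5, N = 184, SD = 2.18 gives z = 0.5 × 13.56 / 4.36 = 1.56 and power 34%. With r² = 0.70, z = 1.30 and power is 26%. With r² = 0.64, power is 24%.

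| b (points per SD) | Numeric, SD 2.18 | Cut | Numeric, SD 2.42 | Cut | Loss (points) |
|---|---|---|---|---|---|
| 0.25 | 12% | 10% | 11% | 9% | 2–3 |
| 0.5 | 34% | 24–26% | 29% | 20–22% | 7–10 |
| 0.6 | 46% | 32–35% | 39% | 27–29% | 10–14 |
| 0.75 | 65% | 46–50% | 56% | 39–42% | 14–18 |
| 1.0 | 88% | 70–74% | 80% | 61–65% | 14–19 |

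The cut columns use r² = 0.64–0.70. At r² = 0.60 (40% loss) the largest power loss is about 22 points. With only the 149 expected completers, the smallest is 1.4.

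**5. Check by simulation.** Simulating the ANCOVA with baseline scores 4–10 cut at 6 (3,000 runs per setting, SD 2.18) gave 12.5% vs 10.0%, 33% vs 23%, 63% vs 48% and 86% vs 72% for b = 0.25, 0.5, 0.75 and 1.0.

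**6. Scale.** With a baseline SD of 1.41, b = 0.25, 0.5 and 1.0 correspond to 0.18, 0.35 and 0.71 point per baseline point. Over scores 4 to 10 the effect then changes by about 1.1, 2.1 and 4.3 points.

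**The case against.** The strongest reply is that nothing here is stated wrongly. The groups are fixed in advance (for CDI, by rule), and the same groups serve for test and display, so the p-value refers to what the reader sees. The onset-age cut has a visible sense, since the trial enrols ages 13–17 and the cut separates onset before that range from onset within it. Treatment differences are shown in every category whatever the interaction result, so a non-significant test suppresses nothing. A linear term gives leverage to patients scoring 9 or 10, and if the effect steps at the cut the split loses nothing.

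Most of that stands. The choice is legitimate and the consequence limited. The larger power losses also need large interactions: at b = 0.5 the effect already changes by about 2.1 points across the score range, against a design difference of 1.0. At b = 0.25 both tests are close to uninformative. What the reply does not remove is that the test called primary for these subgroup analyses uses less of the data than the model already contains, and that no numeric interaction test is planned alongside it.

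A reader might also infer that one percentage and one range of power points apply to all three measures. The SAP supports no such fixed figures, because it gives no distribution, SD or interaction size. The sentence naming the interaction as the primary test belongs to the BPI ANCOVA. CDI sits in a logistic model for events of unstated frequency, so the ANCOVA figures do not carry over to it. Nor does the study-median cut by itself bias the treatment comparison, since it uses baseline scores pooled over arms.

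**Conclusion.** The point holds as a minor improvement. Cutting these measures costs roughly 30–40% of the information about a linear interaction when the cut is near the median, and more when it is off-centre. For baseline pain at N = 184 the power cost is about 1–3 points for small interactions (0.25 point per SD) and about 10–19 for large ones (0.6–1.0 point per SD).

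These figures rest on an approximately linear change in effect, an SD of change of about 2.2–2.4 back-solved from section 5.2, 30–36% information lost, and an assumed distribution of baseline scores. For onset age only the information loss can be bounded, under assumed distributions. For CDI no power figure can be given.

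It might be inferred that the numeric test would be adequately powered, or that the trial's main conclusion is at risk. Neither follows: numeric power is only about 29–34% at 0.5 point per SD, and the primary MMRM comparison is untouched.

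**What to change.** In section 6.1.15:
- **Baseline BPI pain:** base the interaction test on treatment by continuous baseline value in the same ANCOVA. The main effect is already there.
- **Onset age:** enter onset age as a continuous term and test its interaction with treatment.
- **CDI, separately:** use continuous CDI and treatment-by-CDI in the logistic model of suicide-related events.
- **Existing categories:** keep the groups in Table HMGW.6.14 and the CDI median groups to show treatment differences within groups and as a check on linearity.

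The cost is a few lines of SAP wording and one or two changed model terms per variable, with no new data. The downside is that the test assumes an approximately linear change in effect.

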## 6.2. Interim Analysis

Due to low patients enrollment throughout this study, Lilly provided FDA with a document (Sequence No. 0036) to request release from the post marketing requirement (PMR) in April 2014. FDA requested Lilly to explore the possibility of conducting an interim analysis of the efficacy data in their July 2014 written response. Lilly proposed a futility analysis which was

subsequently requested to conduct from FDA. The appropriate Lilly regulatory scientists were consulted and determined that the unplanned interim analysis plan will be documented in the SAP, and the protocol was not amended.

The interim analysis would focus on the primary efficacy analysis of duloxetine 30/60 mg once daily (QD) compared with placebo on the reduction of average pain severity as measured by the BPI average pain severity rating during the Study Period II in adolescents (aged 13 to 17 years) with JPFS. The purpose of the interim analysis is to evaluate the primary efficacy endpoint to stop the study early for futility using pre-specified decision rules, and it will not require adjustment of  $\alpha$ . Sites will remain blinded to any information produced from the interim analysis. A statistical analysis center (SAC), which would be external to the study team in order to maintain data integrity, will be unblinded and conducting the analyses in the restricted access folder, [https://sddchippewa.sas.com/webdav/lillyce/prd/ly248686/f1j\\_mc\\_hmgw/ac\\_unblinded1](https://sddchippewa.sas.com/webdav/lillyce/prd/ly248686/f1j_mc_hmgw/ac_unblinded1). The study team will remain blinded to the interim analysis data if the study continues. The SAC members will not be in contact with study site personnel.

The randomization cut-off date for the interim analysis will be the date when approximately 150 patients are randomized, which is approximately 71% of planned enrollment. The data lock for the interim analysis would occur approximately 3 months later to ensure those randomized patients will subsequently either complete or discontinue the double-blind treatment phase. The patient population for the interim analysis will be all patients randomized on or before the randomization cut-off date.

The futility interim analysis will be based on the calculation of conditional power (CP). Conditional power represents the probability that the ongoing trial will result in statistically significant difference between duloxetine 30/60 mg QD and placebo at end of the trial, based on the data available at the time of interim analysis. The calculation of conditional power follows that proposed in Lan and Wittes (1988) and DeMets (2006). If  $Z(t)$  represents the test statistic at interim, then the conditional power for expected test statistic  $\theta$  (the assumed treatment effect) at end of trial could be calculated as following:

$$CP = 1 - \Phi \left\{ \frac{Z_{\alpha/2} - Z(t)\sqrt{t} - \theta(1-t)}{\sqrt{1-t}} \right\}$$

Where  $\Phi$  is the cumulative distribution function of the standard normal distribution,  $\alpha$  is the type I error for two-sided test, and  $t$  is the information fraction which defined as proportion of planned patients randomized at interim analysis. If assuming data at end of the trial will follow the trend observed at interim analysis, the calculation of conditional power could be simplified as following:

$$CP = 1 - \Phi \left\{ \frac{Z_{\alpha/2} - Z(t)/\sqrt{t}}{\sqrt{1-t}} \right\}$$

The test statistic  $Z(t)$  will be calculated based on estimators from primary efficacy analysis. The primary efficacy analysis will be the contrast between duloxetine 30/60 mg QD and placebo at the last visit during double-blind treatment phase (Visit 8, Week 13) from a mixed model repeated measures analysis (MMRM) on change from baseline in BPI average pain severity. The model will include the fixed categorical effect of treatment, pooled investigate site, visit, and treatment-by-visit interaction, as well as the continuous, fixed covariate of baseline value of BPI average pain severity and baseline value of BPI average pain severity-by-visit interaction. The test statistic at interim will be approximately calculated as  $Z(\hat{t}) = \hat{\delta}/se(\hat{\delta})$ , where  $\hat{\delta}$  is the estimator of the contrast between duloxetine 30/60 mg QD and placebo at Week 13, and  $se(\hat{\delta})$  is the corresponding standard error.

The SAC will only communicate one of the two possible decisions to Lilly:

- Conditional Power (CP)  $<0.6$ : Trial termination for futility
- Conditional Power (CP)  $\geq 0.6$ : Trial may continue

with the pre-determined Lilly individuals (medical director, regulatory scientist, statistician, clinical trial manager, chief operating officer, and clinical project management advisor) in order to decide further study implementation. The outline of the plan will be based on the document that Lilly submitted to FDA on September 2, 2014, containing Lilly responses to the FDA guidance provided in the written responses dated July 11, 2014 titled "Response to FDA's Information Request Regarding Release from Post Marketing Requirement for Adolescents with Fibromyalgia: Study F1J-MC-HMGW" (Sequence No. 0037).

The SAC will inform the FDA project manager of the primary efficacy results from a mixed model repeated measures analysis (MMRM) on change from baseline in BPI average pain severity as well as the conditional power. This will be sent by a password protected encrypted file with a cover letter.

When the CP meets the criterion of futility stopping rule, and the study is terminated early, the sensitivity analyses to address the impact of missing data on primary efficacy analysis may not be performed.

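### The 0.6 futility cut-off is not tied to one conditional power formula, and the 80% power statement leaves the futility rule out

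*SAP*

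**What the plan says.** SAP Section 6.2 describes one unplanned interim look, intended "to stop the study early for futility using pre-specified decision rules". The decision rests on conditional power (CP): below 0.6 means termination, and 0.6 or above means that the trial may continue.

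Two expressions for CP are printed. The general one depends on theta, and its introduction reads "the assumed treatment effect) at end of trial could be calculated as following". No number is given for theta. The second applies if the observed trend is assumed to persist, in which case "the calculation of conditional power could be simplified as following". The section then defines Z(t) as the Week 13 treatment contrast from the primary repeated-measures model divided by its standard error. The 0.6 rule follows and refers only to conditional power, naming neither an expression nor a theta.

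SAP Section 5.2 sets the size at about 184 randomized patients, allows for an 81% completion rate, and states that "this sample size will provide at least 80% power to detect the treatment difference of 1.0 point" at alpha 0.05. It does not mention the futility look.

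**The concern.** A cut-off on conditional power is a complete rule only when the effect assumed for the remaining patients is fixed. Current-trend CP extrapolates the interim estimate. CP under the design effect assumes that the remaining patients behave as planned. For a mildly disappointing interim result the design-effect value is higher, so the same Z can fall on either side of 0.6.

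An early stop also costs power under either version, because some trials that would have ended significant are stopped. A 0.6 cut-off about three quarters of the way through is demanding, so this cost is not negligible. A power statement that ignores it describes a trial without the rule.

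**Working it through.** **Inputs from the SAP.** Two-sided alpha 0.05, so the critical value is 1.960 (Sections 6.1.2 and 6.2). About 184 patients, and at least 80% power for 1.0 point (Section 5.2). Interim at about 150 randomized, stated as about 71% of planned enrollment; t is the proportion of planned patients randomized (Section 6.2).

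**Assumptions.** Unstopped power is exactly 80%, so the design value is theta = 1.960 + 0.842 = 2.802; 85% and 90% are shown below. Section 5.2 gives no standard deviation, so any margin above 80% cannot be checked. Z is taken as positive when duloxetine is better.

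**Information fraction.** The stated 71% does not reproduce: 150/184 = 0.815, while 150/0.71 is about 211 patients. Both values of t are carried.

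**Relation of the two expressions.** In the general form the numerator contains Z√t + theta(1−t). Setting theta = Z/√t gives Z(t + 1 − t)/√t = Z/√t, which is the second expression. The algebra is sound, and only theta is open.

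**Interim Z needed to continue.** Set CP = 0.6, with normal quantile 0.253.

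- Current trend: c = √t × (1.960 + 0.253√(1−t)).
  - t = 0.815: 0.903 × (1.960 + 0.109) = 1.87.
  - t = 0.71: 0.843 × (1.960 + 0.136) = 1.77.
- Design theta: c = (1.960 + 0.253√(1−t) − 2.802(1−t))/√t.
  - t = 0.815: (2.069 − 0.518)/0.903 = 1.72.
  - t = 0.71: (2.096 − 0.812)/0.843 = 1.52.

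Examples: at t = 0.815 and Z = 1.80, CP is 0.53 (trend, stop) or 0.66 (design theta, continue). At t = 0.71 and Z = 1.65, it is 0.50 or 0.67.

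**Chance of opposite decisions if the design effect is real.** The interim Z has mean theta√t and unit variance.

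- t = 0.815: Φ(1.868 − 2.530) − Φ(1.718 − 2.530) = 0.254 − 0.209 = 4.6%.
- t = 0.71: Φ(1.766 − 2.361) − Φ(1.524 − 2.361) = 0.276 − 0.201 = 7.5%.

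The first term in each line is the chance of stopping under the trend rule, and the second is the chance under design theta.

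**Overall power if a stop is obeyed.** This is P(interim Z ≥ c and final Z ≥ 1.960), bivariate normal with means theta√t and theta, unit variances and correlation √t. The design-theta column uses the theta that matches each unstopped power.

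| Unstopped power | t | Trend rule | Design-theta rule |
|---|---|---|---|
| 80% | 0.815 | 71.6% | 74.6% |
| 80% | 0.71 | 68.6% | 73.6% |
| 85% | 0.815 | 77.5% | 80.8% |
| 85% | 0.71 | 74.6% | 80.2% |
| 90% | 0.815 | 83.8% | 87.1% |
| 90% | 0.71 | 81.2% | 86.9% |

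**Splitting the loss at 80%.** The choice of formula accounts for 74.6 − 71.6 = 3.0 points (t = 0.815) or 73.6 − 68.6 = 5.0 points (t = 0.71). Even the milder rule costs 80 − 74.6 = 5.4 or 80 − 73.6 = 6.4 points.

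**If there is no effect.** The rules disagree in Φ(1.868) − Φ(1.718) = 0.969 − 0.957 = 1.2% of trials (t = 0.815), or Φ(1.766) − Φ(1.524) = 0.961 − 0.936 = 2.5% (t = 0.71).

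**The case against.** The best defence is that there is only one rule. The second expression is a special case of the first. Everything that it needs (Z(t), t and alpha) is defined, whereas the general form cannot be run without a theta that the SAP does not supply. Section 6.2 also describes conditional power as resting on the data available at the interim. The phrase could be introduces both expressions and may be no more than style. Much of this stands: current trend is the likelier intention, and the theta of 2.80 used here is derived from Section 5.2, not printed there. It remains an inference, because the general form speaks of an assumed effect and Section 5.2 offers an obvious candidate.

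Three stronger readings are tempting and should not be drawn.

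- **That unblinded staff choose the formula after seeing the data.** Section 6.2 gives the external analysis center no such choice and speaks of a single conditional power. It says that the outline of the plan is based on a document sent to FDA on 2 September 2014, and SAP version 2 was approved in December 2014, before unblinding. That document is not at hand and may settle the point.
- **That the design theta is the right choice.** It keeps more power because it stops less often, and that includes trials with no effect (95.7% against 96.9% stopped at t = 0.815). This is a trade-off, and either choice is legitimate.
- **That the ambiguity causes the whole power loss.** Most of it comes from the 0.6 cut-off under either formula.

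**Conclusion.** The point holds in two parts.

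The smaller part is that Section 6.2 does not name the conditional power compared with 0.6. The two readings disagree for an interim Z of 1.72 to 1.87 (t = 0.815) or 1.52 to 1.77 (t = 0.71), and they agree in at least 92.5% of trials when the design effect is real.

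The larger part is that the power statement in Section 5.2 takes no account of the futility rule. With unstopped power of exactly 80%, obeying a stop leaves 68.6% to 74.6%. From 85% it leaves 74.6% to 80.8%, and from 90% it leaves 81.2% to 87.1%. The stated minimum is therefore kept only if the unstopped design had roughly 85% to 90% power, which the SAP does not show.

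These figures assume that a stop is obeyed and that information accrues with the proportion randomized, as Section 6.2 defines it. Because the look can stop only for futility, it does not inflate type I error.

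**What to change.** In Section 6.2, add one sentence naming the single expression that is compared with 0.6. Current trend is acceptable; if the general form is used, give the value of theta. In Section 5.2, restate the power for a 1.0-point difference that remains under that rule, at an information fraction on which the two sections agree.

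This changes SAP wording and needs a short calculation, with no new data. The cost is that the stated power becomes less favourable.
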